3.0 STUDY RATIONALE

Studying neoadjuvant pembrolizumab therapy is an attractive strategy for studying the immunologic changes caused by PD-1 checkpoint masking. Most of the immunologic activity associated with pembrolizumab occurs in the tumor and surrounding microenvironment. Evaluation of post-pembrolizumab tumor will be important to understanding factors associated with pembrolizumab activity, immune tolerance, and discovery of other targets for immune therapy. Pembrolizumab has

17

The information contained in this document is regarded as confidential, and may not be disclosed to another party unless such disclosure is required to initiate the study, to conduct study-related activities, or to comply with national, state, or local laws and regulations. Written authorization from the coordinating site and sponsor is required for disclosure otherwise.

11 Nov 2018

known benefit in non-small cell lung cancer. The addition of pembrolizumab for two doses prior to surgery and four doses after surgery has the potential to confer clinical benefit. Large randomized phase 3 trials are now testing whether PD-1 checkpoint antibodies improve survival as adjuvant therapy after resection of early stage lung cancer.

At Duke Medical Center, we are conducting an investigator-initiated, neoadjuvant trial of carboplatin, paclitaxel, and ipilimumab in early stage lung cancer. In cases in which there was excess tumor available at surgery, the laboratory of [name] PhD has been able to disaggregate ample quantities of functional tumor infiltrating lymphocytes (TILs) to fully characterize the TIL population and ultimately determine what antigens the TILs are activated against. In other studies, in which Duke Cancer Institute has been a coordinating center, tumor specimens have been shipped on wet ice to arrive within 24 hours of surgery and functional TILs have been successfully collected as part of a multi-center trial in glioblastoma multiforme. One of the most important exploratory, secondary objectives of this trial will be to investigate the methods that would allow assessment of immunologic response to pembrolizumab in the tumor, discover markers of immune therapy resistance, and discover new targets for immune therapy.

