3.2 Trial Design

This is a multi-institution phase 2 trial studying 2 doses of pembrolizumab prior to surgery and 4 doses after surgery for stage IB, II or IIIA non-small cell lung cancer. Patients will undergo standard diagnostic workup and pre-surgical staging for early stage lung cancer. Patients with stage IB (> 3 cm), II or IIIA lung cancer will be eligible. We will require that the primary tumor be > 3 cm in order to improve the chances that there will be adequate excess tumor after surgery for planned correlative science studies.

Studying the tumor microenvironment after pembrolizumab is an important secondary endpoint of this trial. Therefore an additional eligibility requirement regardless of the lung cancer stage will be that the primary tumor will need to be > 3 cm by pre-treatment radiographic measurement. For instance, a T1, N1, Mx stage lung cancer would not be eligible for this trial. The requirement that the tumor is > 3 cm will increase the chances that there will be enough excess tumor at surgery to collect for correlative science studies. It will not be possible to know if N1 nodes are pathologic by clinical staging so requiring tumors to be > 3 cm by clinical staging also creates a study population that has been shown to benefit from preoperative or postoperative systemic therapy.

Eligible patients will have ECOG PS of 0-1, good organ function, and no history of active autoimmune disease. Patients will receive 2 doses pembrolizumab on days 1 and 22. Patients will undergo standard surgical resection approximately 29 – 56 days after initiation of pembrolizumab and at least 2 days after the second dose of pembrolizumab. After recovery from surgery, patients will be evaluated to receive standard chemotherapy.

Patients may receive post-operative radiation according to standard clinical indications such as close or positive tumor margin, or presence of N2 metastases. After completion of all standard therapy patients may receive 4 cycles of adjuvant pembrolizumab. Patients will have follow-up as per institutional standard.

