9.5 Surgery

Surgery to occur at 4-8 weeks (days 29-56) or subject will be removed from trial unless approved by PI. If pembrolizumab dose 2 is delayed, then there should be at least 2 days between pembrolizumab infusion and surgery.

The ability to perform surgery will be assessed by the surgeon and will be based on physical exam and radiological evaluation. Surgical therapy will be individualized based on the surgical judgment and patient preference and is not dictated by study protocol. Excess tumor tissue samples will also be collected at time of surgical resection after determination that adequate tumor has been taken by surgical pathology for all standard clinical studies. Specific instructions for processing and shipping are provided in Appendices G & H.

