11.1 Treatments Administered

Patients will receive pembrolizumab as follows:**

Neoadjuvant Pembrolizumab: Cycle 1 day 1: pembrolizumab 200 mg IV

Cycle 2 day 1 (21 days after cycle 1 day 1): pembrolizumab 200 mg IV

Pembrolizumab will be administered as a 30-minute IV infusion (treatment cycle may be delayed up to 3 weeks due to toxicity). Sites should make every effort to target infusion timing to be as close to 30 minutes as possible. However, given the variability of infusion pumps from site to site, a window of -5minutes and +10 minutes is permitted (i.e., allowed infusion time is between 25 and 40 minutes).

Surgery: Standard surgical evaluation to occur after the last dose of pembrolizumab followed by surgical therapy.

Adjuvant chemotherapy: Is a standard consideration as per NCCN guidelines. Patients will be evaluated and offered adjuvant chemotherapy based on standard criteria such as T > 3 cm and/or metastases in N1 and/or N2 lymph nodes. Adjuvant chemotherapy is not study specific and should be given by commercial supply and standard of care.

Adjuvant radiation: Is sometimes a standard consideration as per NCCN guidelines. Patients will be evaluated and offered radiation based on standard criteria such as positive post-operative tumor margin and/or presence of metastases in N2 lymph nodes. Adjuvant radiation is not specific to this study and should be given as per standard of care.

Adjuvant Pembrolizumab: Three to 6 weeks after completion of all standard therapy including adjuvant chemotherapy and/or radiation therapy, patients will receive pembrolizumab 200 mg IV every 21 days for 4 doses.

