11.4 Pembrolizumab Dose Modifications

Adverse events (both non-serious and serious) associated with pembrolizumab exposure may represent an immunologic etiology. These adverse events may occur shortly after the first dose or several months after the last dose of treatment. Pembrolizumab must be withheld for drug-related toxicities and severe or life-threatening AEs as per Table 1 below.

If pembrolizumab is delayed more than two weeks due to a related AE, then pembrolizumab will be discontinued and patients should proceed to surgical resection when clinically appropriate.

Table 1
Dose Modification Guidelines for Drug-Related Adverse Events

Toxicity	Hold Treatment For Grade	Timing for Restarting Treatment	Treatment Discontinuation
Diarrhea/Colitis	2-3	Toxicity resolves to Grade 0-1.	Toxicity does not resolve within 12 weeks of last dose or inability to reduce corticosteroid to 10 mg or less of prednisone or equivalent per day within 12 weeks.
	4	Permanently discontinue	Permanently discontinue
AST, ALT, or Increased Bilirubin	2	Toxicity resolves to Grade 0-1	Toxicity does not resolve within 12 weeks of last dose.
	3-4	Permanently discontinue (see exception below)	Permanently discontinue
Type 1 diabetes mellitus (if new onset) or Hyperglycemia	T1DM or 3-4	Hold pembrolizumab for new onset Type 1 diabetes mellitus or Grade 3-4 hyperglycemia associated with evidence of beta cell failure.	Resume pembrolizumab when patients are clinically and metabolically stable.
Hypophysitis	2-4	Toxicity resolves to Grade 0-1 Therapy with Pembrolizumab can be continued while endocrine replacement therapy is instituted	Toxicity does not resolve within 12 weeks of last dose or inability to reduce corticosteroid to 10 mg or less of prednisone or equivalent per day within 12 weeks.
	4		
Hyperthyroidism	3	Toxicity resolves to Grade 0-1	Toxicity does not resolve within 12 weeks of last dose or inability to reduce corticosteroid to 10 mg or less of prednisone or equivalent per day within 12 weeks.
	4	Permanently discontinue	Permanently discontinue
Hypothyroidism	2-4	Therapy with pembrolizumab can be continued while thyroid	Therapy with pembrolizumab can be continued while thyroid

Toxicity	Hold Treatment For Grade	Timing for Restarting Treatment	Treatment Discontinuation
		replacement therapy is instituted	replacement therapy is instituted.
Infusion Reaction	3-4	Permanently discontinue	Permanently discontinue

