20.5 Immediate Reporting of Serious Adverse Events

20.5.1 Serious Adverse Events

A serious adverse event is any adverse event occurring at any dose or during any use of Merck's product that:

- Results in death;
- Is life threatening;
- Results in persistent or significant disability/incapacity;
- Results in or prolongs an existing inpatient hospitalization;
- Is a congenital anomaly/birth defect;
- Is another important medical event
- **Note:** In addition to the above criteria, adverse events meeting either of the below criteria, although not serious per ICH definition, are reportable to the Merck in the same timeframe as SAEs to meet certain local requirements. Therefore, these events are considered serious by Merck for collection purposes.

- Is a new cancer (that is not a condition of the study);
- Is associated with an overdose.

Refer to Table 6 for additional details regarding each of the above criteria.

For the time period beginning when the consent form is signed until treatment allocation/randomization, any serious adverse event, or follow up to a serious adverse event, including death due to any cause other than progression of the cancer under study that occurs to any subject must be reported within 24 hours to the Duke Sponsor (DCI Safety Desk) who will report within 2 working days to Merck Global Safety if it causes the subject to be excluded from the trial, or is the result of a protocol-specified intervention, including, but not limited to, washout or discontinuation of usual therapy, diet, placebo treatment or a procedure.

For the time period beginning at treatment allocation/randomization through 90 days following cessation of treatment, or 30 days following cessation of treatment if the subject initiates new anticancer therapy, whichever is earlier, any serious adverse event, or follow up to a serious adverse event, including death due to any cause other than progression of the cancer under study whether or not related to the Merck product, must be reported within 24 hours to the Duke Sponsor (DCI Safety Desk) who will report within 2 working days to Merck Global Safety.

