- 1) Whether the cumulative percentage of deaths among all treated patients related to any of the study treatments from the first pembrolizumab treatment until 30 days after surgery exceeds 17%.
- 2) If the cumulative percentage of all treated patients deemed unable to go to surgery due to adverse events attributed to neoadjuvant therapy exceeds 20%. The percentage of patients unable to go to surgery after pembrolizumab is a conservative estimate based on data reported for a SWOG trial that studied neoadjuvant chemotherapy in early stage lung cancer (22).

The first 10 treated patients will be evaluated for safety and feasibility. If in the first ten patients the criteria for overall therapy being not safe or feasible is met, accrual to the study will be suspended to allow for investigation. After consideration by the study team and the IRB, a decision will be made as to whether accrual can be resumed, potentially with modifications to entry criteria and/or study conduct. In addition, all toxicity patterns will be monitored by the DCI Safety Oversight Committee.

The trial will be stopped for accrual whenever a total of 35 patients are registered or at least one of the thresholds of the safety and feasibility criteria is exceeded. In the event either of these two thresholds is exceeded, the investigational therapy will be considered “infeasible” in this setting.

Accrual and follow-up

With an expected rate of 2 patients being enrolled each month, the trial will take about 16 months to reach the target accrual. All registered patients will be followed for tumor response, disease free survival and overall survival.

Statistical Analysis Plan

Surgery feasibility rate, the primary endpoint of the trial, will be analyzed using the data from all evaluable patients, who are defined as the patients who meet eligibility criteria and has received at least 1 dose of pembrolizumab. The surgery feasibility rate of neoadjuvant pembrolizumab as well as its confidence interval will be estimated.

Secondary Objectives

All secondary objectives are considered exploratory in nature, and type I error will not be controlled for multiplicity. P-values for these statistical tests will be provided for descriptive purposes. However, if a statistical test on a secondary outcome is significant at the 2-sided significance level of 0.01, the finding will be considered worthy of future investigation.

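### The only numeric death limit closes 30 days after surgery, leaving the adjuvant phase (four of six planned pembrolizumab doses) reviewed but with essentially no numeric limit

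*Combined protocol and SAP*

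**What the plan says.** Section 27.1 sets two numeric safety and feasibility criteria. The first concerns the "cumulative percentage of deaths among all treated patients" that are "related to any of the study treatments from the first pembrolizumab treatment until 30 days after surgery exceeds 17" percent. The second is a 20% limit on treated patients who cannot go to surgery because of adverse events attributed to neoadjuvant therapy. The first ten treated patients are checked, and accrual is suspended if a criterion is met. After that, accrual stops whenever a threshold is exceeded, and the investigational therapy is then to be considered infeasible. The text introducing the criteria says that they judge pembrolizumab followed by surgery.

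The regimen is longer than that. Section 3.0 describes "The addition of pembrolizumab for two doses prior to surgery and four doses after surgery". Section 3.2 says "Patients will receive 2 doses pembrolizumab on days 1 and 22". Section 9.5 says "Surgery to occur at 4-8 weeks (days 29-56) or subject will be removed from trial unless approved by PI". Under Section 11.1, three to six weeks after all standard therapy, "patients will receive pembrolizumab 200 mg IV every 21 days for 4 doses". Section 9.8 puts the latest adjuvant start at 4, 6 or 8 months after surgery, depending on which other adjuvant therapy was given.

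On late toxicity, Section 11.4 says of pembrolizumab-associated adverse events: "These adverse events may occur shortly after the first dose or several months after the last dose of treatment". Section 20.5.1 makes serious adverse events, including deaths other than from progression, reportable "through 90 days following cessation of treatment", or for 30 days if new anticancer therapy starts, whichever is earlier. Serious events considered related are reportable at any time. Section 27.1 sends toxicity patterns to a safety oversight committee, and Section 15.2 lists the incidence or severity of adverse drug reactions as a ground for ending the trial. Neither carries a number.

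**The concern.** The rule gives its verdict on the investigational therapy but counts deaths over only the first part of it. A pembrolizumab-related death in the adjuvant phase adds nothing to criterion 1, and it cannot enter criterion 2, which is only about reaching surgery. Two related deaths among the first ten patients would be 20%, above the limit, if they fell before day 30 after surgery. In the adjuvant phase the same two deaths would leave criterion 1 at 0%. Because the rule is cumulative and runs throughout accrual, early patients can be receiving adjuvant doses while others are still being enrolled. What is at stake is whether those deaths can trigger a pre-specified halt to accrual or depend wholly on judgement.

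**Working it through.** **Plan's own figure.** The plan gives no operating characteristics for the 17% limit. Its only computed figure is the 84.6% power of the primary test. That reproduces as Φ(0.15/√(0.8×0.2/30) − 1.036) = 0.8455, and it does not bear on this point.

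**1. When the window closes.** Surgery day + 30: 29 + 30 = 59 and 56 + 30 = 86. Measured from dose 2 on day 22: 59 − 22 = 37 and 86 − 22 = 64 days.

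**2. Where the adjuvant doses fall.** Take 4, 6 and 8 months as 122, 183 and 244 days, with dose 4 coming 63 days after dose 1.

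| Adjuvant start after surgery | Dose 1, days after window closes | Dose 4, days after window closes |
|---|---|---|
| 3 weeks (no other adjuvant therapy) | 21 − 30 = −9 | 54 |
| 4 months | 122 − 30 = 92 | 155 |
| 6 months | 183 − 30 = 153 | 216 |
| 8 months | 244 − 30 = 214 | 277 |

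Only in the first row does one adjuvant dose fall inside the window, and doses 2-4 still fall outside. Otherwise 4 of 6 planned doses (67%) lie outside.

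**3. Overlap with accrual.** Section 27.1 expects 2 patients a month for about 16 months. Assume adjuvant dosing starts 3 to 10 months after first dose. The 3 is an assumption. The 10 is roughly day 56 + 244 = day 300. Patients enrolled early enough: (16 − 10) × 2 = 12 and (16 − 3) × 2 = 26. Applying the surgery rates in the plan's hypotheses: 12 × 0.65 = 7.8 and 26 × 0.80 = 20.8, so about 8 to 21. If accrual runs to 35 patients (35/2 = 17.5 months), the range is 15 × 0.65 = 9.8 to 29 × 0.80 = 23.2. Removals under Section 9.6 and refusals lower either range.

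**4. How much a short window can hide.** The smallest counts above 17% are 2 of 10, 4 of 20, 6 of 30 and 6 of 35. The table gives exact binomial probabilities. The total death rates over the whole regimen, and the shares falling inside the window, are my assumptions. The last column checks after every patient from the 10th to the 35th.

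| Assumed total rate | Share counted | ≥2 of 10 | ≥6 of 35 | Any crossing, 10-35 |
|---|---|---|---|---|
| 10% | all | 0.264 | 0.132 | 0.399 |
| 10% | half | 0.086 | 0.007 | 0.120 |
| 10% | one third | 0.042 | 0.001 | 0.056 |
| 15% | all | 0.456 | 0.431 | 0.685 |
| 15% | half | 0.170 | 0.044 | 0.249 |
| 15% | one third | 0.086 | 0.007 | 0.120 |
| 20% | all | 0.624 | 0.728 | 0.872 |
| 20% | half | 0.264 | 0.132 | 0.399 |
| 20% | one third | 0.140 | 0.027 | 0.202 |

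The rows in which all deaths count treat each death as known at once. Late deaths arrive when more patients are in the denominator, so before accrual closes those figures are upper bounds.

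**The case against.** The strongest reply is that the scope is deliberate and stated. The primary objective is surgical feasibility, and the criteria are introduced as judging pembrolizumab followed by surgery, so a perioperative death window matches the question asked. That stands: criterion 1 is not an error and need not be replaced. It does not explain why a perioperative count should decide a label placed on the investigational therapy, or why the rest of the regimen has no limit of its own.

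The second reply is that later deaths are not ignored. A reader might infer that they never count at all, or that the plan would declare the regimen safe. The documents support neither. Deaths are reportable under 20.5.1, the sponsor monitors aggregated safety data (20.7), the committee reviews toxicity patterns, 15.2 gives a termination ground, and 15.4 lets the PI-sponsor or IRB stop at any time. Criterion 1 can only suspend or stop accrual, or label the therapy infeasible. What is missing is a threshold.

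Other stronger readings also fail:

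- Section 11.4 warns of late adverse events. It does not name deaths.
- Not every adjuvant dose is outside the window, as step 2 shows, nor does every one follow chemotherapy or radiation.
- The 12 to 26 patients in step 3 are those enrolled early enough. They are not those who will actually receive adjuvant doses.
- For patients never operated on, the window has no stated end. That is a missing detail, not evidence that their deaths are left out.

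Finally, simply stretching criterion 1 would carry a real cost. Adjuvant dose 4 falls on about day 113-363, so 90 days later is day 203-453. Waiting for that in the first ten patients could push the early look to or beyond the end of accrual.

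**Conclusion.** The point holds as a coverage gap in a safety rule, not as an arithmetic error or a contradiction. The only numeric death limit closes on day 59-86. Four of six planned doses then fall under no numeric limit, with the one exception shown in step 2. The gap matters during accrual for at most about 8 to 21 patients on Section 27.1's 16-month accrual, given the assumed 3-10 month start and a 65-80% surgery rate, and for fewer after removals. The probabilities in step 4 rest on assumed death rates and shares. They show direction and possible size, and they do not predict mortality in this trial. Reporting and committee review limit the harm, so this is an inexpensive safety improvement and not a flaw that undermines the design.

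How many patients enter the adjuvant phase is itself unclear. Section 9.6 removes patients with positive margins or N2 disease from protocol, while Sections 9.8 and 11.1 describe adjuvant pembrolizumab after radiation. Those sections must be reconciled.

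**What to change.** Keep criterion 1 and the first-ten look unchanged, named as the neoadjuvant-plus-surgery criterion. Add to Section 27.1 a parallel cumulative criterion:

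- **Count:** pembrolizumab-related deaths among all treated patients, as they occur, from first dose to 90 days after the last pembrolizumab dose received in either phase.
- **Patients not operated on:** the same end date.
- **Attribution:** deaths attributed only to standard chemotherapy or radiation are tabulated separately.
- **Threshold:** apply the existing 17% accrual-stop threshold, or state the sponsor's own with its exact binomial operating characteristics.

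Because accrual already stops whenever a threshold is exceeded, the new count needs no extra look and does not delay the early one. No new data are needed. Section 20.5.1 already covers 90 days, or 30 if new anticancer therapy starts, and related serious events are reportable at any time.

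The costs are wording and three limitations that should be stated. The limit can fire somewhat more often: on step 4's assumptions, a 10% total rate with half the deaths now counted goes from 0.120 to at most 0.399 for any crossing. Late deaths are divided by all treated patients, including some not yet exposed to adjuvant doses; with 20 treated, 4 deaths are needed to exceed 17%. Some adjuvant follow-up will mature only after accrual closes, when the count can inform the conclusion but no longer the accrual decision.

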27.0 STATISTICAL METHODS AND ANALYTICAL PLANS

27.1 Statistical Considerations

Sample size justification

Futility Analysis

Futility analysis is often used for assessing clinical efficacy before the trial reaches target accrual and stops the trial early if the therapy clearly performs worse than control. The primary objective of this one-arm phase II trial is not to evaluate the efficacy of pembrolizumab in this population. Since it is unlikely that the therapy will harm the patients, a futility analysis on the percentage of patients with adequate TIL collection is unnecessary.

Evaluation of Investigational Therapy Safety and Feasibility

Analytic methods

Overview

The primary objective of the single arm phase II trial is to determine whether the surgery feasibility rate of neoadjuvant pembrolizumab is not significantly worse than the historical surgical feasibility rate of neoadjuvant chemotherapy. Surgery feasibility rate of a neoadjuvant therapy is the percent of patients who are able to undertake surgery after the neoadjuvant therapy. A total of 30 evaluable patients will be entered to the single arm trial. Taking 15% rate of cancellation and ineligibility into account, the trial will enroll a total of 35 patients and eligible subjects (not screen failures) will be followed for 2 years for both disease recurrence and death. Following that, patients will be followed every 6 months for up to five years.

Primary Objective Sample Size Justification

According to Pisters et al (JCO 2010), approximately 80% of subjects undergo surgical exploration within 42 days of day 1 of the last cycle of standard neoadjuvant chemotherapy. We would like to test the following hypotheses:

$$H_0: p \geq 0.80 \text{ vs. } H_a: p \leq 0.65$$

where p is the true surgery feasibility rates after combined neoadjuvant chemotherapy and pembrolizumab. With 30 evaluable patients receiving protocol treatment, the study has approximately 84.6% power rejecting $H_0: p \geq 0.80$ when $p = 0.65$ at one-sided significance level of 15%.

Adverse event monitoring: In this trial design it is difficult to accurately attribute adverse events to pembrolizumab, surgery, or other causes. Further, the analysis of treatment toxicities as isolated events will not best represent whether or not the combination of pembrolizumab followed by surgery is safe and feasible. Therefore, this safety and feasibility trial will be evaluated by the following criteria:

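### Both safety and feasibility criteria in Section 27.1 count only treatment-attributed events, although the section calls accurate attribution difficult; criterion 2 also states its basis in unattributed terms

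*Combined protocol and SAP*

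**What the plan says.** Under adverse event monitoring, Section 27.1 of the combined protocol and SAP states: "In this trial design it is difficult to accurately attribute adverse events to pembrolizumab, surgery, or other causes". It adds that toxicities taken as isolated events would not represent the safety and feasibility of the sequence well. From these two reasons it derives two criteria:

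- **Criterion 1** counts "deaths among all treated patients related to any of the study treatments". The window opens at the first dose and closes 30 days after the operation, and the limit is 17%, taken cumulatively.
- **Criterion 2** is the cumulative percentage of treated patients "deemed unable to go to surgery due to adverse events attributed to neoadjuvant therapy exceeds 20"%.

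On the second limit the plan says: "The percentage of patients unable to go to surgery after pembrolizumab is a conservative estimate based on data reported for a SWOG trial". It cites reference 22 for this, but the list in Section 28.0 ends at 14. No source is given for the 17%.

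The first ten treated patients are reviewed, and meeting a criterion there suspends accrual for investigation. Accrual also stops whenever either limit is exceeded, up to 35 registered patients, and the therapy is then called infeasible. No crossing probabilities are stated.

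The primary endpoint needs no attribution: "Surgery feasibility rate of a neoadjuvant therapy is the percent of patients who are able to undertake surgery after the neoadjuvant therapy".

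**The concern.** The section gives unreliable attribution as a reason for the criteria and then makes both depend on attribution. Criterion 1 pools all study treatments, so nobody has to separate pembrolizumab from surgery, but deaths judged due to other causes are left out. Criterion 2 has no pooling: a patient who misses surgery because of an adverse event assigned to infection, comorbidity or tumour is not counted.

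Attribution is made open-label (Section 12.0). The Section 20.8 guidance for a related event is that the product is the more likely explanation, so an ambiguous event need not count. Attributed events are a subset of all events, so this count can never exceed the any-cause count.

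Criterion 2 has a second problem. Its numerator is restricted to attributed adverse events, while the sentence supporting the limit describes patients who cannot reach surgery, without that restriction.

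These are the only numeric safety stops in the plan, and crossing one decides whether the therapy is labelled infeasible.

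**Working it through.** **The plan's own figures.** There are no operating characteristics for the 17% and 20% limits to reproduce. The nearby 84.6% power belongs to the primary test ("With 30 evaluable patients receiving protocol treatment"). It reproduces as Φ(0.15/√(0.80×0.20/30) − 1.036) = 0.8455 and says nothing about these limits.

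**Inputs from Section 27.1.** Limits of 17% and 20%; first review at 10 treated patients; stop whenever a limit is exceeded; 30 evaluable and at most 35 registered.

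**Assumptions, not in the documents.** The true event rates; the share of events attributed; each outcome known before the next check; checking starts at patient 10.

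**Smallest counts that exceed a limit.**

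| n | deaths >17% | unable to have surgery >20% |
|---|---|---|
| 10 | 2 | 3 |
| 30 | 6 | 7 |
| 35 | 6 | 8 |

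**Method.** A single look uses P(X ≥ c | n, p), X binomial. For the whenever-exceeded rule, let f_n(k) be the probability of k events in n patients without an earlier crossing:

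f_n(k) = (1−p)·f_{n−1}(k) + p·f_{n−1}(k−1)

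At every n ≥ 10, paths with k/n above the limit are removed. The crossing probability is the total removed.

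**Criterion 2, true AE-related non-surgery rate 30%.** If one third are assigned elsewhere, the counted rate is 0.30 × 2/3 = 0.20.

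| Counted rate | n=10 only | n=30 only | every patient, 10–30 | every patient, 10–35 |
|---|---|---|---|---|
| 30% (all counted) | 62% | 84% | 95% | 96% |
| 20% (two thirds counted) | 32% | 39% | 70% | 73% |

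A range for the share, at the plan's own unacceptable rate of 35% not operated, checking every patient from 10 to 30:

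| Share attributed | Counted rate | Crossing |
|---|---|---|
| 100% | 35% | 98% |
| 75% | 26.25% | 89% |
| 50% | 17.5% | 59% |
| 25% | 8.75% | 15% |

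**Criterion 1, true death rate 20%.** With one third assigned elsewhere, the counted rate is 0.20 × 2/3 = 13.3%. Checking every patient from 10 to 35, crossing is 87% if all are counted and 60% if two thirds are.

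**Cost of counting all deaths.** At a true all-cause rate of 3%, the first-10 review gives 1 − 0.97¹⁰ − 10×0.03×0.97⁹ = 3.5%. Checking every patient gives 4.6%. If only 2% are counted as related, checking every patient gives 2.1%.

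**Cost of widening criterion 2 at an unchanged 20%.** Suppose related adverse events prevent surgery in 5% and unrelated ones in another 5%. Checking every patient from 10 to 30, crossing rises from 3.5% (counted rate 5%) to 20% (counted rate 10%). If every patient not operated for any reason were counted, a trial at the plan's acceptable 20% non-surgery rate would cross about 70% of the time.

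**The case against.** Counting treatment-related events is a legitimate way to judge whether a therapy is infeasible. The text says attribution is difficult, not impossible, and gives a second reason for the criteria. Criterion 1 avoids the hardest separation by pooling treatments. Section 20.8 sets structured causality guidance, and Section 19.4 asks for events of unknown cause to be evaluated as possibly immune-related, which can push towards attribution. The primary endpoint counts non-surgery whatever the cause, the Safety Oversight Committee sees all toxicity patterns, and Section 15.2 allows early termination. All of this stands, and it limits the damage. It does not supply a numeric interim trigger free of attribution.

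Four stronger readings are tempting but not supported:

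- *That 20% is the all-cause historical loss, so attributed failures alone must exceed it.* It is the complement of the 80% in the null hypothesis, but that 80% is a timing figure: "approximately 80% of subjects undergo surgical exploration within 42 days of day 1 of the last cycle of standard neoadjuvant chemotherapy". Its complement can include patients explored later. Reference 22 is not listed, so what it counts cannot be checked.
- *That the limits fire too rarely.* No target is stated and the attributed share is unknown. Single looks at 30 patients exaggerate the loss: at a counted rate of 17.5% they give 26%, against 59% under the whenever-exceeded rule.
- *That the mismatch also affects the 17% limit.* The plan gives no benchmark for 17%.
- *That attribution errors can only favour continuing.* Over-attribution is possible. What is certain is only that an attributed count cannot exceed an any-cause count.

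**Conclusion.** The concern holds in a limited form. Both criteria rest on the judgement that the section calls difficult, and criterion 2 counts something narrower than the quantity used to support its limit. These two statements come from the text and need no assumption.

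The effect is a lower chance of crossing than an any-cause count would give. With one third of events assigned elsewhere, it falls from about 95% to 70% for criterion 2 (true rate 30%) and from about 87% to 60% for criterion 1 (true rate 20%). The rates and the share are illustrative assumptions. The size of the effect in this trial cannot be derived from the documents.

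For criterion 1 the remedy is cheap. For criterion 2, widening the count at the same limit is a real trade-off.

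**What to change.** **Criterion 1.** Count every death from the first pembrolizumab dose to 30 days after surgery, whatever the attribution. Keep investigator attribution as a listing for the Safety Oversight Committee. The change is one phrase. Section 20.5.1 already brings in deaths other than from progression, whether or not related. Deaths from progression are exempt from that route (Section 20.7), so sites would have to notify those in the window. The statistical cost is a crossing probability of about 4.6% at a true 3% death rate, against about 2.1% if 2% are counted as related.

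**Criterion 2.** Make the numerator and the basis of the 20% refer to the same events. There are two ways:

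1. Keep the attributed count, and give a basis for 20% that concerns adverse-event failures attributed to neoadjuvant therapy.
2. Count patients who cannot have surgery because of any adverse event. Then re-confirm the limit, since 20% may no longer suit, and state crossing probabilities for the first-10 review and for the whenever-exceeded rule. In the example above, false crossing rises from about 3.5% to 20%, and the consequence is a label of infeasible.

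List reference 22 and state what its percentage counts. Until then, do not write that 20% is the all-cause historical figure.
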